## 1. SYNOPSIS

**Protocol Title:** An open-label, randomised, single-dose, two-period cross-over study to evaluate bioequivalence of GR37547 ciprofloxacin 500 mg tablet versus ciprofloxacin 500mg tablet reference product in healthy adult participants under fasting conditions

**Short Title:** Bioequivalence study between GR37547 500 mg tablet versus ciprofloxacin 500mg tablet reference product in healthy adult participants under fasting conditions.

### Rationale:

This study will determine if ciprofloxacin 500 mg tablets (test formulation: GR37547; CIPVAL™; GlaxoSmithKline Pakistan Limited) are bioequivalent to ciprofloxacin 500 mg tablets (reference formulation: Ciproxin; Bayer Limited, United Kingdom).

### Objectives and Endpoints:

Objectives	Endpoints
Primary  To determine if 500 mg Ciprofloxacin (GR37547) tablets are bioequivalent to reference 500 mg Ciprofloxacin tablets in healthy adult participants under fasting conditions.	Plasma PK parameters: $AUC_{(0-t)}$ and $C_{max}$ , for ciprofloxacin in relevant treatments.
Secondary  To assess secondary PK parameters of 500 mg ciprofloxacin tablets (GR37547) relative to reference 500 mg ciprofloxacin in healthy adult participants under fasting conditions.  To compare the safety and tolerability of a single dose of a 500 mg ciprofloxacin tablet (GR37547) with reference 500 mg ciprofloxacin tablet, in healthy adult participants under fasting conditions.	
 
Plasma PK parameters: <math>AUC_{(0-\infty)}</math>, <math>t_{max}</math>, <math>\%AUC_{ex}</math> and <math>t_{1/2}</math> for ciprofloxacin in relevant treatments.
 
Adverse events (AE), clinical laboratory values (Haematology and Biochemistry), ECGs and vital signs
 

AUC(0-∞)= Area under the concentration-time curve from time zero (pre-dose) extrapolated to infinite time; %AUCex= Percentage of AUC(0-∞) obtained by extrapolation; AUC(0-t)= Area under the plasma concentration versus time curve from time zero to t, where t is the time of the last quantifiable concentration; t1/2= Terminal phase half-life; Cmax= Maximum observed concentration; Tmax= Time of occurrence of Cmax.

### Overall Design:

This is a Phase I, open label, balanced, randomised, single dose, two-way crossover study, enrolling 26 healthy participants at a single centre.

Each enrolled study participant will take part in two treatment periods in accordance with the randomisation schedule. The treatment periods will be separated by a washout period of at least 7 days and no more than 14 days.

**Number of Participants:**

Approximately 26 participants will be randomized to yield at least 22 evaluable participants completing the study.

**Treatment Groups and Duration:**

The total duration in the study for each participant is expected to be up to approximately 5 - 7 weeks, from screening to their last visit.

Study treatments will be referred to as Test and Reference throughout the protocol:

- **Treatment A – Test: GR37547 (CIPVALTM), ciprofloxacin 500 mg tablets.**
- **Treatment B - Reference: Ciproxin, ciprofloxacin 500 mg tablets.**

**Treatment Groups and Sequences:**

- Participants will be randomised to one of two sequences, and administered a single oral dose of one of the two treatments (A or B) in each treatment period, such that each participant receives a dose of each treatment in the study.

**2. SCHEDULE OF ACTIVITIES (SOA)**

Details of study assessments and collection windows are given in [Table 1](#)

**Table 1 Schedule of Activities**

Procedure	Screening (Day -21 to Day -1)	Treatment Periods 1 and 2			Follow-up (within approximately 7 days post last dose or at discontinuation)	Notes
		Day -1	Day 1	Day 2		
Informed consent	X					
Inclusion and exclusion criteria	X	X				Refer to Section 6 . Recheck clinical status before randomization. and
Admission to the Unit (domiciled)		X	X	X		Participants to be admitted on Day -1 of each treatment period, and discharged on Day 2.
Outpatient Visits	X					
Discharge				X		
Participants will be discharged from the unit after the collection of the 24 hour post dose PK sample, vital signs (VS), lab assessments and, urinalysis; following review by a doctor to assess participant safety.
 
At the end of treatment period 2, in addition to the other assessments taken at 24 hours post dose (Day 2), all participants will also have an ECG and urine pregnancy test (females), prior to discharge.
 
Participants who have normal safety assessment results at the end of treatment period 2 do not require a follow up.

Procedure	Screening (Day -21 to Day -1)	Treatment Periods 1 and 2			Follow-up (within approximately 7 days post last dose or at discontinuation)	Notes
		Day -1	Day 1	Day 2		
Follow up (Phone Call or Outpatient Visit)					X	If a participant's safety assessments (medical exam, VS, ECG, Lab assessments) are abnormal and clinically significant at Treatment Period 2 discharge, then a follow up phone call or outpatient clinic visit is required within 7 days. Enquiries on the participant's general health, including any AEs/SAEs/concomitant medication should be recorded in the medical notes.
Demography and Medical history (includes substance usage)	X					Substances: Drugs, Alcohol, tobacco and caffeine
Full physical examination including height and weight	X	X				Abbreviated physical exam (excluding height and weight) performed at Day -1
Past and current medical conditions	X	X				
Pregnancy test (WOCBP only)	X	X		X		Serum $\beta$ -hCG: at screening. Urine $\beta$ -hCG: at Day-1 and at the end of Treatment period 2 on Day 2 .
HIV, Hepatitis B and C screening	X					Testing for Hepatitis B (HBsAg) and Hepatitis C (HepC antibody) at screening is not required if this was performed within 3 months prior to first dose of study treatment. Participants, who are positive for Hepatitis C antibody due to prior resolved disease, must have a confirmatory negative Hepatitis C RNA test.

Procedure	Screening (Day -21 to Day -1)	Treatment Periods 1 and 2			Follow-up (within approximately 7 days post last dose or at discontinuation)	Notes
		Day -1	Day 1	Day 2		
Laboratory assessments (include liver chemistries)	X	X		X		
Screening: Participants are required to fast at least 10 hours prior to the Screening Laboratory assessment. Haematology, Biochemistry, glucose -6-phosphate dehydrogenase, Coagulation profile (PT and aPTT) and Urinalysis are assessed.
 
Day -1: Haematology, Biochemistry and Urinalysis are assessed.
 
Day 2: Haematology, Biochemistry and Urinalysis samples are obtained 24 hours post dose, prior to discharge. Additional safety labs must be collected as deemed necessary at the Investigator's discretion.

Urine Drug/Urine Cotinine/Breath alcohol	X	X				
12-lead ECG a	X		X	X		
12-lead ECG will be completed at:
 
 
• Screening,
 
• Day 1: ECG 2h post dose ( <math>t_{max}</math> ) to be completed before vital signs and 2 hour PK sample.
 
• Day 2: at discharge, at the end of Treatment Period 2 prior to the last PK sample
 
• Follow up: only required if the ECG at discharge was abnormal and clinically significant ECGs to be taken <math>\pm 30</math>min of time points specified
 

Procedure	Screening (Day -21 to Day -1)	Treatment Periods 1 and 2			Follow-up (within approximately 7 days post last dose or at discontinuation)	Notes
		Day -1	Day 1	Day 2		
Vital signs a	X		X	X		
Vitals will be taken at:
 
 
• Screening,
 
• Day 1: pre-dose and post dose at, 2.00, 4.00, and 6.00 hours
 
• Day 2: 24.00 hours post-dose.
 
 
Post dose vitals to be taken <math>\pm</math>30min of each time point.

Randomization			X			Day 1 of treatment period 1 only.
Study treatment			X			Screening and Day -1 results must be reviewed by physician prior to randomisation and dosing. Participants to be fasted 10.00 hours prior and 4.00 hours post dose. Dosing between Treatment periods will be separated by a washout of 7 -14 days. Participants will remain in a sitting or semi-supine position for at least 4 hours after dosing on Day 1 of each treatment period.
AE Review		$\leftarrow-----\rightarrow$				Collected from the start of dosing (Day 1, Treatment period 1) to the participant's final discharge from study at the end of Treatment Period 2, follow up call or last outpatient visit, whichever is the latest.
SAE review		$\leftarrow-----\rightarrow$				Any SAEs assessed as related to study participation (e.g. investigational product, protocol-mandated procedures, invasive tests) or related to a GSK concomitant medication will be recorded from the time a participant consents to participate in the study up to and including any follow up contact.

Procedure	Screening (Day -21 to Day -1)	Treatment Periods 1 and 2			Follow-up (within approximately 7 days post last dose or at discontinuation)	Notes
		Day -1	Day 1	Day 2		
Concomitant medication review		←=====→				
Pharmacokinetics a			X	X		
Day 1: Pre-dose, 0.50, 0.75, 1.00, 1.25, 1.50, 1.75, 2.00, 2.50, 3.00, 3.50, 4.50, 6.00, 8.00, 12.00, 18.00 hours
 
Day 2: 24.00 hours post dose
 
Pre-dose sample will be taken within 15 minutes before dose. Post dose samples for:
 
 
• 0.500 -2.00 hours will be taken <math>\pm 2</math> min; ;
 
• 2.50 – 8.00 hours will be taken <math>\pm 5</math> min; and
 
• 12.00 – 24.00 hours will be taken <math>\pm 10</math> min.
 

a. The order of assessments to be followed where an ECG, Vital Signs and Blood sample for either PK or Lab assessments are required at the same time point, should always be first ECG, second vital signs and lastly blood sampling, whilst ensuring that the timing for PK blood samples remains within the sampling window.

- Any changes in the timing or addition of time points for any planned study assessments must be documented and approved by the relevant study team member and then archived in the sponsor and site study files, but will not constitute a protocol amendment. The Institutional review board (IRB)/ Independent ethics committee (IEC) and regulatory authority will be informed of any safety issues that require alteration of the safety monitoring scheme or amendment of the informed consent form (ICF).
- AE= Adverse Event; aPTT= Activated Partial Thromboplastin Time; ECG= Electrocardiogram; GSK= GlaxoSmithKline; HIV= Human Immunodeficiency Virus; hr= Hour; IP= Investigational Product; PK= Pharmacokinetic; PT= Prothrombin Time; SAE= Serious adverse event(s)

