Gastrointestinal reactions	Warning: Nausea and diarrhoea are the most commonly reported adverse drug reactions with Ciprofloxacin treatment. Cases of painful oral mucosa, oral candidiasis, dysphagia, intestinal perforation, gastrointestinal bleeding and loss of	Participants will be monitored closely, and appropriate therapy initiated immediately if any symptoms appear. Participants will be asked to contact the site if any symptoms appear within 24 hours after discharge.

Potential Risk of Clinical Significance	Summary of Data/Rationale for Risk	Mitigation Strategy
	
appetite has also been reported. Vomiting, abdominal pain, dyspepsia and flatulence although uncommon (<math>\geq 1/1000</math> to <math>1/100</math>) have been reported. Severe and persistent diarrhoea may occur during or after treatment (including several weeks after treatment). The antibiotic associated colitis could be life threatening with a fatal outcome. Very rare cases of pancreatitis (<math><1/10000</math>) have been reported.
	
Renal and urinary reactions	
Warning: Rare Cases (<math>\geq 1/10000</math> to <math><1/1000</math>) of renal failure, crystalluria, haematuria, tubulointerstitial nephritis have been reported.
	
Healthy participants with normal renal function as determined by review of creatinine clearance, at screening will be enrolled.
 
Participants will be advised to stay well hydrated in the 24 hours following dosing.

Hepatobiliary reactions	
Warning: Cases of hepatic necrosis and life threatening hepatic failure have been reported with ciprofloxacin.
 
Patients with previous liver damage may have an increase in transaminases, alkaline phosphatase or cholestatic jaundice.
	
Participants will be closely monitored for 24 hours following treatment and advised to immediately report any signs and symptoms of hepatic disease such as anorexia, jaundice, dark urine, pruritus or tender abdomen. Laboratory biochemistry results will be reviewed for increases in transaminases, alkaline phosphatase or bilirubin. Any increases to <math>> ULN</math> from baseline levels, following the first dose, will result in discontinuation from further dosing of study treatment based on PI discretion.

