## 5. STUDY DESIGN

### 5.1. Overall Design

This is a Phase I, open label, balanced, randomised, single dose, two-way crossover study, enrolling approximately 26 healthy participants at a single centre.

Each enrolled study participant will participate in two treatment periods in accordance with the randomisation schedule. The treatment periods will be separated by a washout period of at least 7 days and no more than 14 days.

**Figure 1** Study Schematic

Study participants will be randomised to one of two treatment sequences (A-B or B-A). A single dose of one of the two treatments A or B, will be administered on Day 1, in each treatment period. Each participant will participate in both treatment periods and receive a single dose of each treatment.

Study treatments will be referred to as Test and Reference throughout the protocol:

- **Treatment A – Test: GR37547 (CIPVALTM), ciprofloxacin 500mg tablets.**
- **Treatment B - Reference: Ciproxin, ciprofloxacin 500mg tablets.**

Treatment periods 1 and 2 will be separated by a washout period of 7 to 14 days.

The total duration in the study for each participant is expected to be 5 to 7 weeks, from screening to their last visit.

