### **9.2.1. Time Period and Frequency for Collecting AE and SAE Information**

- All SAEs will be collected from the time a participant consents to participate in the study until the follow-up visit at the time points specified in the SoA (Section 2).
- AEs will be collected from the start of IP administration and until the follow-up contact at the time points specified in the SoA (Section 2).
- Medical occurrences that begin before the start of study treatment but after obtaining informed consent will be recorded on the Medical History/Current Medical Conditions section of the case report form (CRF) not the AE section.
- All SAEs will be recorded and reported to the sponsor or designee within 24 hrs, as indicated in [Appendix 4](#). The investigator will submit any updated SAE data to the sponsor within 24 hrs of it being available.
- Investigators are not obligated to actively seek AEs or SAEs in former study participants. However, if the investigator learns of any SAE, including a death, at any time after a participant has been discharged from the study, and he/she considers the event to be reasonably related to the study treatment or study participation, the investigator must promptly notify the sponsor.

The method of recording, evaluating, and assessing causality of AEs and SAEs and the procedures for completing and transmitting SAE reports are provided in [Appendix 4](#).

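### When Period 2 discharge results are normal, AEs are actively sought for 7 to 14 days after dose 1 but only about 24 hours after dose 2, so late-onset AEs are probably under-counted on both products

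*Combined protocol and SAP*

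**What the plan says.** Four parts of the plan set the AE window.

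- **Section 2, Table 1, AE Review row.** Collection starts with dosing in Period 1 and ends at the participant's "final discharge from study at the end of Treatment Period 2, follow up call or last outpatient visit, whichever is the latest".
- **Section 2, Table 1, Discharge and Follow up rows.** Discharge is on Day 2, after the 24-hour sample and safety checks. "Participants who have normal safety assessment results at the end of treatment period 2 do not require a follow up". A call or visit within 7 days is required only if a result is abnormal and clinically significant.
- **Section 5.1.** "The treatment periods will be separated by a washout period of at least 7 days and no more than 14 days". Table 1 has participants readmitted on Day -1 of Period 2, so every participant who continues has a site contact 6 to 13 days after dose 1.
- **Section 9.2.1.** "AEs will be collected from the start of IP administration and until the follow-up contact at the time points specified in the SoA". This refers back to Table 1. The section adds that "Investigators are not obligated to actively seek AEs or SAEs in former study participants". The exception applies "if the investigator learns of any SAE, including a death, at any time after a participant has been discharged from the study", and only if the investigator considers the event reasonably related to study treatment or participation.

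Section 3.3.1, Table 2 gives participants some reporting advice. In the gastrointestinal row, "Participants will be asked to contact the site if any symptoms appear within 24 hours after discharge". Other rows ask for immediate reporting of visual or hearing disturbance and of signs of liver disease or haemolysis.

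**The concern.** Comparing safety and tolerability is a secondary objective (Section 4, Table 3), and AEs are summarised by treatment in the Safety Population (Section 10.3.5 and Appendix 6). In that summary a Period 2 dose counts as much as a Period 1 dose, although it is actively watched for a much shorter time. An AE that starts on day 3 will be asked about after dose 1. After dose 2, in a participant with normal discharge results, nobody asks.

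The plan itself shows interest in the days after discharge:

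- The gastrointestinal contact instruction covers the 24 hours after discharge, when the AE window of these participants has already closed.
- Section 9.2.5 collects pregnancies to 5 days after the last dose, but these participants have no contact at which to ask.
- Section 9.4.4 deals with clinically significant laboratory values up to 7 days after the last dose.
- Table 2 describes diarrhoea several weeks after treatment and tendon cases several months after it.

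AEs that have started by Period 2 discharge are inside the window and are not part of this point.

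**Working it through.** The plan gives no figure for AE coverage, so there is none to reproduce. A late AE here means one that starts after discharge, about 24 hours after a dose. I assume that an AE counts against the most recent dose.

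**Inputs.** There are 13 participants in each sequence (Section 7.3, Table 5). Doses are 7 to 14 days apart and discharge follows the 24-hour sample (Table 1). Half-life is 4 to 7 hours (Section 3.2). The share *f* of participants with a follow-up after Period 2, and the late-AE rate *q* per dose, are not in the documents and are assumed.

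**1. Window per dose.** It is 7 to 14 days after dose 1 and about 1 day after dose 2 with normal results, a 7- to 14-fold difference.

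**2. Doses actively watched beyond 24 hours.** Each product is given first to 13 participants and second to 13. The share watched is (13 + 13*f*)/26 = (1 + *f*)/2:
- *f* = 0: 13/26 = 50%
- *f* = 10%: 55%
- *f* = 20%: 60%

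If exactly 22 complete in balance and *f* = 0, it is 11/22 = 50%.

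**3. Balance between products.** Each product has 13 first-period and 13 second-period doses, so the expected shortfall is the same for both.

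**4. Drug left at 24 hours.** Simple decay gives 2^(-24/4) = 1.6% and 2^(-24/7) = 9.3%. Most AEs driven by exposure should therefore start inside the window. The loss concerns delayed reactions.

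**5. What the shorter window could cost.** With *f* = 0, the chance of seeing at least one late AE on a product is 1 - (1 - *q*)^n, where n is the number of doses actively watched. The expected number of late AEs after all Period 2 doses is 26*q*.

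| Assumed *q* | n = 13 | n = 26 | 26*q* |
|---|---|---|---|
| 0.1% | 1.3% | 2.6% | 0.026 |
| 1% | 12% | 23% | 0.26 |
| 5% | 49% | 74% | 1.3 |
| 10% | 75% | 94% | 2.6 |

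The two lower rates are included because most of the frequencies that Table 2 gives are at or below 1%. Table 2 gives no rate for nausea or diarrhoea, so the upper rows cannot be excluded.

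**The case against.** The strongest reply is that this is a deliberate, risk-based choice. The Table 1 rows agree with each other. Section 3.3 calls the safety profile well established, and Section 3.3.1 expects mostly uncommon or rare risks to be rarer still after one dose in healthy volunteers. The decay figures support a short window. No late-AE rate, confidence bound or safety test is planned, and the assumed rates have no source in the documents. A day-7 call would also miss diarrhoea weeks later and tendon problems months later.

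Most of this stands, and it makes the point an inexpensive improvement, not a flaw in the study's main conclusion. It does not remove the unequal window.

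Three stronger readings are tempting, and the documents do not support them:

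- **Period 2 doses can yield no late AE, so late-AE rates are exactly halved.** Passive routes remain: the 24-hour gastrointestinal instruction, the advice in Table 2 to report certain signs immediately, and related SAEs that the investigator learns of. Table 1 does not say whether a call made by the participant extends the AE window.
- **The overall AE rates are halved.** Only AEs starting after discharge are affected, and their share is unknown.
- **The test-reference comparison is biased.** The sequences are balanced, so both products lose the same coverage in expectation.

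**Conclusion.** The concern holds in limited form. Active collection of late AEs covers about half of each product's doses: 50% if nobody needs follow-up after Period 2, and 55 to 60% if an assumed 10 to 20% do. This rests on balanced completion. Late AEs are probably under-counted in the by-treatment summary for both products. The number lost cannot be derived from the documents and may be very small. The plan also leaves open whether symptoms reported after Period 2 discharge become AE data. Pharmacokinetics, bioequivalence and the test-reference comparison are untouched. The change is worth making because it is cheap and serves a stated secondary objective.

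**What to change.** **Preferred: three edits to Table 1.**

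1. Follow up row: require a phone call to every participant about 7 days after the Period 2 dose, asking about AEs, concomitant medication and pregnancy, in addition to any earlier contact for abnormal results.
2. Discharge row: say that participants with normal results need only this call.
3. AE Review row: end collection at this call or the last outpatient visit, whichever is later.

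**Cost.** At most 26 calls, with no added visit, examination or sample. The last participant's end date moves about 6 days later (day 7 instead of day 1 after the dose). The call fits the existing follow-up column, and 21 + 14 + 7 = 42 days, or 6 weeks, lies within the stated 5 to 7 weeks. It also gives the 5-day pregnancy collection a contact.

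**Limits.** The call only roughly matches the 7 to 14 days after dose 1 and will not reach events weeks or months later.

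**If no call is added.** State in the AE Review row that symptoms reported after Period 2 discharge are recorded as AEs. Add an AE summary by treatment limited to onset within 24 hours of each dose, so that all 52 doses share one window. This costs one sentence and one table. The table makes the doses comparable but recovers no late events.

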### 3. INTRODUCTION

#### 3.1. Study Rationale

GSK Product, GR37547 (Ciprofloxacin) 500 mg tablets is marketed in Pakistan as CIPVAL™. This study is required to determine whether the test product GR37547/CIPVAL™ is bioequivalent to the reference ciprofloxacin 500 mg tablets in healthy adult participants. Bioequivalence (BE) will be declared if the 90% confidence interval (CI) for the true ratio of test to reference geometric means falls entirely within the range of 0.80 to 1.25 for all primary PK parameters.

